### **7.2.11 Recording and Reporting Adverse Events**

#### **7.2.11.1 Process for Recording Adverse Events**

##### Dose-limiting toxicities (DLTs)

DLTs will be entered into Oncore within 5 calendar days of the study team learning of the event. DLTs that are deemed serious and unexpected will be submitted to the IRB per institutional guidelines (see below).

##### Other AEs

AEs must be recorded into the University of Virginia Cancer Center OnCore database per the following guidelines:

**Product:** Pembrolizumab

**Protocol/Amendment No.:** UVA Breast 48

V04-13-21

Table 9: Recording AEs into the OnCore Database

High Risk Studies								
Reporting requirements for AEs that occur within 30 days of the last dose of protocol specified treatment								
	Grade 1	Grade 2		Grade 3				Grade 4 & 5
	Expected and unexpected	Expected	Unexpected	Expected	With hospitalization	Without hospitalization	With hospitalization	Expected and Unexpected
Unrelated Unlikely	OnCore 30 days a	OnCore 30 days	OnCore 30 days	OnCore 30 days	OnCore 15 days	OnCore 30 days	OnCore 15 days	OnCore 7 days
Possible Probable Definite	OnCore 30 days a	OnCore 30 days	OnCore 15 days	OnCore 30 days	OnCore 15 days	OnCore 7 days	OnCore 7 days	OnCore (24-hrs)* 7 days

\*Enter into OnCore database within 24 hours if unexpected and definitely related to protocol specified treatment  
Hospitalization defined as an inpatient hospital stay or prolongation of a hospital stay equal to or greater than 24 hours  
a Grade 1 unexpected or expected hematologic/metabolic events will be recoreded in the Cancer Center Database; however, regardless of attribution, these events do not have to be reported.

### 7.2.11.2 Recording Laboratory Values

Laboratory values specified in [Table 6](#) will be recorded in the UVA Cancer Center database, graded using the CTCAE v4.03 (if a grading category exists) and reported as described in [Section 7.2.11](#). Any abnormal laboratory values captured which are not included in the list, but are considered to be pertinent positive clinical signs/symptoms will be recorded in the UVA Cancer Center database and reported as described in [Section 7.2.11](#). If there is any doubt on the part of study personnel concerning what constitutes a pertinent positive finding, the Sponsor-Investigator will be consulted.

### 7.2.11.3 UVA IRB Reporting Requirements

The University of Virginia is responsible for reporting to the UVA IRB-HSR per the following guidelines:

**Product:** Pembrolizumab

**Protocol/Amendment No.:** UVA Breast 48

V04-13-21

**Table 10: UVA IRB-HSR Reporting**

Type of Event	To whom will it be reported:	Time Frame for Reporting	How reported?
Any internal event resulting in death that is deemed DEFINITELY related to (caused by) study participation (Note: An internal event is one that occurs in a subject enrolled in a UVa protocol.)	IRB-HSR	Within 24 hours	IRB Online and phone call www.irb.virginia.edu/
Internal, Serious, Unexpected adverse event.	IRB-HSR	Within 7 calendar days from the time the study team received knowledge of the event.  Timeline includes submission of signed hardcopy of AE form.	IRB Online www.irb.virginia.edu/
For Device Studies: Unanticipated adverse device effects (internal)	IRB-HSR	Within 10 day calendar days of the study team receiving knowledge of the event	IRB Online www.irb.virginia.edu/
Unanticipated Problems that are not adverse events or protocol violations This would include a Data Breach.	IRB-HSR	Within 7 calendar days from the time the study team received knowledge of the event.	Unanticipated Problem report form. http://www.virginia.edu/vprgs/irb/HSR_docs/Forms/Reporting_Requirements-Unanticipated_Problems.doc
Protocol Violations ( The IRB-HSR only requires that MAJOR violation be reported, unless otherwise required by your sponsor, if applicable. )  Or  Enrollment Exceptions	IRB-HSR	Within 7 calendar days from the time the study team received knowledge of the event.	Protocol Violation and Enrollment Exception Reporting Form  http://www.virginia.edu/vprgs/irb/hsr_forms.html
Data Breach	The UVa Corporate Compliance and Privacy Office and  ITC: if breach involves electronic data-  UVa Police if breach includes such things as stolen computers.	As soon as possible and no later than 24 hours from the time the incident is identified.  As soon as possible and no later than 24 hours from the time the incident is identified.  IMMEDIATELY.	UVa Corporate Compliance and Privacy Office- [contact]  ITC: Information Security Incident Reporting procedure , http://www.itc.virginia.edu/security/reporting.html  Phone- [contact]

**Product:** Pembrolizumab

**Protocol/Amendment No.:** UVA Breast 48

V04-13-21

#### **7.2.11.4 Reporting to the FDA**

The Sponsor-Investigator for the study (the UVA PI or designee) is responsible for providing safety updates to the FDA per the following guidelines. The reporting times refer to the time the study team received knowledge of the event.

FDA Reporting Requirements for Pembrolizumab related adverse events

- Serious and unexpected suspected adverse reactions will be reported to the FDA no later than 15 calendar days after the sponsor determines that the requirements for an IND safety report have been met. The FDA will be notified using an FDA Form 3500a.
- Unexpected fatal or life-threatening suspected adverse reactions will be reported to the FDA no later than 7 calendar days after the Sponsor receives the initial information of the event. The FDA will be notified using an FDA Form 3500a.

Other adverse event information will be sent to the FDA in the IND annual report.

FDA Reporting Requirements for HIFU: Unanticipated adverse device effects (UADE)

- Unanticipated adverse device effects (UADEs) will be reported to the FDA no later than 10 calendar days after the Sponsor-Investigator receives the initial information of the event.

Other adverse event information will be sent to the FDA in the IND annual report.

#### **7.2.11.5 Reporting to the Echopulse Manufacturer**

All unanticipated adverse device effects (UADEs) will be reported to the Echopulse Manufacturer (Theraclion) no later than 5 calendar days after the Sponsor-Investigator receives the initial information of the event.

### **7.2.12 Sponsor Responsibility for Reporting Adverse Events**

All Adverse Events will be reported to regulatory authorities, IRB/IECs and investigators in accordance with all applicable global laws and regulations.

## **8.0 STATISTICAL ANALYSIS PLAN**

### **8.1 Statistical Analysis Plan Summary**

This is a pilot study of high intensity focused ultrasound (HIFU) and pembrolizumab, and is proposed as a pilot two-arm design. All patients will receive the FDA approved dosing of pembrolizumab and allocation to arms is randomized. Participants from arm A will first receive HIFU ablation and then a pembrolizumab infusion 1 week after an ablative procedure. Participants from arm B will first receive pembrolizumab at baseline and then undergo the HIFU ablation two weeks later. The goal is to obtain preliminary data on the safety of HIFU and pembrolizumab and to obtain estimates of change in immune parameters (proportion of activated CD8 tumor infiltrating lymphocytes (TILs) is primary) pre- and post-treatment. The trial will not be powered for cross arm comparison, but will nevertheless provide useful pilot data for the design of a larger trial of combined therapies.

Safety stopping rules will be employed within each study arm and will be judged by dose limiting toxicities (DLTs), defined in [Section 7.2.10](#). The primary objectives include assessing adverse events

**Product:** Pembrolizumab

**Protocol/Amendment No.:** UVA Breast 48

V04-13-21

and change in the proportion of CD8+ to CD4+ tumor infiltrating lymphocytes (TILs) in the primary ablation zone. Secondary endpoints include assessing change in CD8+ T-cell responses at peri-ablation zones, clinical responses at local and distant metastatic sites, disease free survival (DFS), and overall survival (OS). Exploratory endpoints include assessing change in T-cells in peripheral blood, markers of T-cell activation, gene expression profiling, and enumeration of myeloid derived suppressor cells.

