## 2.0 TRIAL DESIGN

### 2.1 Trial Design

This is a two-arm pilot study of High-Intensity Focused Ultrasound (HIFU) and immunotherapy. The goals of the study are to obtain preliminary data on the safety of HIFU with immunotherapy, delivered concurrently, and to obtain preliminary estimates of change in T-cell frequency and activation for HIFU alone (day 15-21 of ARM A) and pembrolizumab and HIFU given in combination (day 15-21 of arm B). The central hypothesis is that focused energy induced immunogenic cell death will overcome limitations in antigen availability, and effective T-cell responses, and thereby enhance immune-therapy of advanced breast cancer. Our secondary hypothesis is that concomitant immune-activation will further augment CD8+ T-cell responses to tumor antigen released by HIFU. We will obtain preliminary data on whether HIFU promotes the presence of CD8+ T-cells in ablated primary tumors, blood and non-ablated distant metastases. Additional correlative science endpoints will be tested as exploratory endpoints.

[figure not shown]
Eligible subjects will be randomized 1:1 to the investigational treatments (Arm A) or (Arm B). Subjects on both arms will undergo HIFU treatment on day 15. Subjects randomized to Arm A will receive pembrolizumab administered IV every 3 weeks on days 22, 43, and 64. Subjects randomized to Arm B will receive pembrolizumab administered IV every 3 weeks on days 1, 22, 43 and 64. In all subjects, restaging breast cancer-dedicated chest, abdomen and pelvic CT scan will be performed at baseline and cycle 4. Biopsies of tumors treated with HIFU will be completed on all patients at days 1 and 22 with optional distant tumor site biopsies and additional biopsies of the HIFU treated breast lesion to be completed at day 64. The tissue removed at the biopsies will be evaluated as part of the immunologic correlative studies.

**Product:** Pembrolizumab

**Protocol/Amendment No.:** UVA Breast 48

V04-13-21

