## 3.0 OBJECTIVES & HYPOTHESES

### 3.1 Primary Objectives & Hypotheses

**Objective:** To determine whether the addition of pembrolizumab to HIFU increases the proportion of CD8+ tumor infiltrating lymphocytes (ratio CD8+/CD4+) in the primary ablation zone of advanced or metastatic breast cancer.

**Hypothesis:** Focused energy induced immunogenic cell death is hypothesized to improve antigen availability, dendritic cell activity, effective T-cell responses. In combination with pembrolizumab, it is hypothesized that CD8+/CD4+ ratio in the ablation zone will increase by 25%.

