It is observed that sub-ablative tumor disruption by FUS is novel and immunologically relevant. Sub-ablative FUS treatment results in recognition of a larger array of epitopes than surgery in clinical and preclinical studies (16, 25, 27). FUS combined with immunotherapy in mice results in increased myeloid, NK and T cell responses locally and systemically compared to either modality alone (20, 25-30). FUS alone was shown to induce immune response in tumors and specifically, sub-ablative FUS achieved controlled apoptosis with efficient antigen delivery to DC's; NK and TIL infiltrations were also enhanced (25, 26, 29, 31). FUS is also believed to help prevent T cell tolerance (15). FUS stimulates T cell infiltration into breast tumors as shown by studies examining the microenvironment (15, 16, 32, 24, 25).

Additionally, HIFU may enhance drug delivery to the tumor site. FUS increases capillary leakage and local chemokine release, thus augmenting drug delivery and T-cell trafficking (25, 33-35). Additional rationale is that anti-PD-1 antibodies and FUS have largely non-overlapping toxicities. The toxicities for both treatments are minimal. FUS is non-invasive and performed with mild sedation (20, 30, 31).

We are currently studying HIFU in breast fibroadenomas and bone metastases from any solid tumor (NCT02078011 and NCT00656305). No serious AE's have been seen in over 200 patients treated with HIFU for breast diseases to date. HIFU is safer and easier to contour than other ablative therapies. Other therapies produce spherical ablation zones, whereas HIFU can be contoured and carefully tuned to sub-ablative power for individual tumors. Patients and providers are motivated by these technical improvements (27).

**Product:** Pembrolizumab

**Protocol/Amendment No.:** UVA Breast 48

V04-13-21

In this pilot study, we will test pembrolizumab therapy in combination with HIFU to assess for enhanced immune stimulation and antitumor effects at local ablation sites, distant, non-treated sites and in the blood. Biopsy data from before and after therapy with pembrolizumab and HIFU will demonstrate both immunologic and tumor responses to the combined therapy proposed. We will examine the tissue in the peripheral zone of ablation as well as distant metastatic sites for CD8 and CD4 T cells with additional analyses of MDSC's, T-regulatory cells and cytokine responses as tissue quantity permits.

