#### **4.4 Rationale for Endpoints**

This study is designed primarily to test whether interfering with immune suppression by blocking the molecular interaction between the PD-1 receptor and its cognate ligand, PD-L1, increases the number and activation of TILs that are induced by the local ablative therapy.

The study is also designed to examine the safety of HIFU and pembrolizumab. HIFU therapy for breast lesions and breast cancer is generally well tolerated. Based on our experience at UVA (n=20) there has been no evidence of grade 4 toxicities in patients who received HIFU. Pembrolizumab has been studied in numerous clinical trials to date and was found to be well tolerated with no dose-limiting toxicities at the standard dose of 200 mg (see Investigator's Brochure). Our proposed study is the first study to combine HIFU and pembrolizumab in humans and safety is our secondary endpoint.

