## 8.2 Statistical Analysis Plan

Target sample size is 12 participants, which was chosen as a feasible number that could be accrued within a 2 year accrual period. Participants will be randomized 1:1 to treatment arms A and B with block randomization using blocks of size 2 or 4. Participants are considered evaluable if they satisfy all inclusion and exclusion criteria and have adequate endpoint measurements during respective cohort timelines. Adjusting for a 10% unevaluable/drop-out rate, maximum target accrual is estimated at 15 participants.

The purpose is to assess the adverse events profile of pembrolizumab and focused ultrasound therapy and estimate the difference in the TILs at baseline and 3 weeks within each arm, not to make definitive comparisons between arms. With 6 participants per arm, there is limited power to make comparisons between arms. Lu et. al. (2009) data estimates the difference in means of the ratio of CD4+ and CD8+ cells for patients treated with HIFU versus no HIFU to be 0.57, with standard deviations ranging from 0.27 to 0.40. These data provide an indication of the magnitude that could be detected in this study at baseline and 3 weeks, where it is assumed that the no HIFU participants in Lu et. al. are comparable to baseline measurements in our study. Using these data as a guideline, with n=6, we have 80% power to detect an effect size of 1.44 for the within-arm change in ratio of CD4+ and CD8+ cells at baseline and 3 weeks. Depending on the variability of the data, this is equivalent to detecting differences of 0.39 and 0.58, for assumed standard deviations of 0.27 and 0.40, respectively. The populations will include all intention to treat participants.

Safety stopping rules will be employed within each arm and will be judged by dose limiting toxicities (DLT). If the first two participants within an arm or 3 out of the 6 participants within an arm experience a DLT, that arm will be deemed too toxic and further accrual to that arm will be closed. This decision rule is based on Wald's sequential probability ratio test assuming lower and upper DLT proportions of 0.1 and 0.3, respectively, and type I and II error rates of 10%.

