Adverse events and DLTs will be summarized by frequency and magnitude for each arm and overall. Change in the proportion of CD8+ to CD4+ tumor infiltrating lymphocytes (TILs) in the primary ablation zone will be estimated by arm. Additionally change in CD8+ T-cell responses at peri-ablation zones and clinical response at local and distant metastatic sites measured by abscopal tumor shrinkage at non-ablated sites, will be estimated for each arm. The Kaplan Meier estimator will be used to estimate survival curves for DFS and OS. Exploratory endpoints including change in T-cells in peripheral blood, markers of T-cell activation, gene expression profiling, and enumeration of myeloid derived suppressor cells will be estimated by arm.

If highly favorable responses are seen in this pilot patient population, then this study may be expanded by means of an amendment to more rigorously define response criteria in either or both arms.

**Product:** Pembrolizumab

**Protocol/Amendment No.:** UVA Breast 48

V04-13-21

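### Section 8 conflicts with Section 3 on the primary variable, the survival endpoint and the measure of response, and has no between-arm estimate for the primary question

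*Combined protocol and SAP*

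**What the plan says.** **Primary variable.** Section 3.1 asks whether adding pembrolizumab to HIFU raises the CD8+/CD4+ TIL ratio "in the primary ablation zone of advanced or metastatic breast cancer". The first paragraph of 8.1 says the "proportion of activated CD8 tumor infiltrating lymphocytes (TILs) is primary". The second paragraph of 8.1 returns to CD8+ against CD4+ TILs, and 8.2 says that the change in CD8+ to CD4+ "tumor infiltrating lymphocytes (TILs) in the primary ablation zone will be estimated by arm". Activation sits in a lower tier in 8.1 and in 8.2: "Exploratory endpoints including change in T-cells in peripheral blood, markers of T-cell activation, gene expression profiling". Two background sections still give it weight. Section 2.1 wants "preliminary estimates of change in T-cell frequency and activation for HIFU alone", and 4.4 asks whether PD-1 blockade "increases the number and activation of TILs that are induced by the local ablative therapy". The power statement in 8.2 claims "80% power to detect an effect size of 1.44 for the within-arm change in ratio of" CD4+ and CD8+ cells, without saying which is the numerator.

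**Survival.** Objective 3.3(3) is PFS. Sections 8.1 and 8.2 name only disease-free survival (DFS) and overall survival.

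**Response.** Objective 3.3(2) asks for RECIST 1.1 response on CT at local and distant sites, and Section 11.3 adopts RECIST 1.1. Section 8.2 measures both by abscopal shrinkage at sites that were not ablated.

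**Between-arm estimate.** Section 4.4.1 plans a difference between the two treatment groups in post-treatment tissue biomarkers, and 3.3(1) wants peri-ablation ratios compared between arms. Section 8.2 estimates everything by arm and disclaims definitive comparisons.

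**The concern.** A reader who follows Section 8 literally could report a primary result on activated CD8 cells, draw a survival curve for an endpoint that no objective names, and describe response at the ablated lesion with a measure taken elsewhere. The activated share of CD8 cells and the CD8+/CD4+ ratio are different measurements and need not move together. In an open-label study with a target of 12 participants, a second candidate primary variable and an undefined survival endpoint leave room to choose after the data are seen. Section 8.1 intends the results to inform a larger trial, so it should be plain which quantity was primary. The question in 3.1, what pembrolizumab adds, also needs a contrast that Section 8 never computes.

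**Working it through.** **1. Which variable does the power statement support?** Inputs from 8.2: n=6, effect size 1.44, SDs 0.27 and 0.40. The significance level is not stated; two-sided 5% is assumed. A paired t-test (df=5, noncentral t) gives power 0.803 at 1.44, and 80% power at 1.43 SD. A one-sided 5% test would give 1.19 SD, and a two-sample test with 6 per arm 1.80 SD. So the figure is a two-sided within-arm calculation. In units of the ratio:

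- 1.44 × 0.27 = 0.39
- 1.44 × 0.40 = 0.58

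Both match the plan. They apply to a ratio of CD4+ and CD8+ cells. No effect or SD is given for activated CD8 TILs. An SD does not carry over when a ratio is inverted, so its direction must be fixed.

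**2. What can each biopsy compare?** Inputs: pembrolizumab days in Table 3 (Section 5.2), biopsy days in 2.1 and 6.1, and the rule in 5.2.3 that treatment follows that day's procedures.

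| Biopsy | Arm A before biopsy | Arm B before biopsy |
|---|---|---|
| Day 22 (mandatory) | HIFU only | pembrolizumab day 1, HIFU day 15 |
| Day 64 (optional) | HIFU, pembrolizumab days 22 and 43 | HIFU, pembrolizumab days 1, 22 and 43 |

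At day 22 the contrast between arms is HIFU alone against HIFU plus pembrolizumab, which is the question in 3.1. It is not pembrolizumab before against after HIFU, which is the question in 3.3(1). Only the optional day-64 tissue comes after both orders of treatment, and by then arm B has had one more dose (3 against 2).

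**3. Precision of the day-22 between-arm difference.** Half-width = t(10, 0.975) × SD × √(2/6), with t = 2.228:

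- SD 0.27: 2.228 × 0.27 × 0.577 = 0.35
- SD 0.40: 2.228 × 0.40 × 0.577 = 0.51

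This takes the plan's SDs as SDs of the change, as its own power statement does. It supports description only.

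**4. DFS or PFS.** Sections 5.1.1 and 5.1.2 admit only metastatic or unresectable disease that is at least evaluable, so no participant starts disease-free, and DFS is not defined. The pieces for PFS exist: RECIST 1.1 (11.3), confirmation of progression (5.8.1) and disease follow-up (5.8, 7.1.6.4). Section 8 lacks PFS itself, its origin, its event date and its censoring rule. Under 5.8.1 a confirming scan comes at least 4 weeks (28 days) after the first:

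- first seen at day 64: 64 − 1 = 63 days, or at least 63 + 28 = 91; 28/63 = 44%
- first seen at the next scan, 12 weeks later (64 + 84 = day 148): 148 − 1 = 147 days, or at least 175; 28/147 = 19%

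**5. Response.** Shrinkage at non-ablated sites contains no information on the ablated lesion, so the local half of 3.3(2) has no measure in 8.2. Criterion 2 in 5.1.2 does not require disease measurable by RECIST, and criterion 6 requires only one lesion suitable for HIFU. Some participants may therefore have no measurable disease, or no other lesion.

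**The case against.** The strongest reply is that one parenthesis in a summary does not reopen the primary endpoint. The rest of Section 8 uses the CD4/CD8-type ratio and calls activation exploratory. PFS and response are exploratory in Section 3, in about 12 participants, and DFS may be a slip for PFS. RECIST 1.1 stands in 3.3(2) and 11.3, and 4.4.1 already states a between-group estimate. All of this stands, and it limits the impact. It does not remove the conflicts: 8.1 still names another variable as primary, correcting DFS to PFS still leaves origin, event date and censoring open, and 8.2 carries neither RECIST nor the 4.4.1 difference into the analysis.

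Some stronger readings are not supported:

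- *The ablation zone is undefined.* Section 4.2.6 might suggest this: "We will examine the tissue in the peripheral zone of ablation as well as distant metastatic sites for CD8 and CD4 T cells". That is rationale text. The flow-chart note on the cycle 2 biopsy separates central from peri-ablation passes, and Section 8 lists the two zones as separate endpoints.
- *The PFS clock starts 14 or 21 days apart in the two arms.* That follows only if it starts at first trial treatment (day 15 against day 1) or first pembrolizumab (day 22 against day 1). The documents propose neither, Day 1 is common to both arms (6.1, 7.1.6.2), and no between-arm survival test is planned.
- *Dating shifts PFS by 44% in general.* That holds at the first on-study scan only. Repeat imaging is optional under 5.8.1 and not required in clinically unstable participants.
- *The differing rank labels matter.* Adverse events are primary in 8.1 and secondary in 3.2 and 4.4, but this changes no planned analysis.

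**Conclusion.** The concern holds, with moderate impact. Three conflicts stand in current text: activated CD8 against CD8+/CD4+ as primary, DFS against PFS, and local response measured away from the ablated lesion. In addition, Section 8.2 gives no between-arm estimate, although 3.1 and 4.4.1 call for one.

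A reader might infer that the primary result is left wholly open; the balance of the text favours CD8+/CD4+. A reader might also infer that a between-arm comparison at day 22 would satisfy 3.3(1). It would not, because arm A has had no pembrolizumab by then.

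The reproduced power assumes two-sided 5%. The half-widths of ±0.35 to ±0.51 assume 6 evaluable participants per arm and that the plan's SDs apply to the change. The shift of at least 28 days applies only where a confirming scan is done.

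**What to change.** 1. **Primary variable.** Delete the activated-CD8 parenthesis in 8.1. Name one primary variable: the CD8+/CD4+ TIL ratio in the primary ablation zone, day 1 to day 22. Write the ratio in the same direction in 3.1, the power statement and 8.2, checking the cited SDs against their source. Keep activation exploratory and align 2.1 and 4.4. Keep the within-arm change by arm, and add the between-arm difference in that change with a 95% CI, labelled descriptive, as HIFU plus pembrolizumab against HIFU alone.
2. **Survival.** Replace DFS with PFS in 8.1 and 8.2. Define the event as RECIST 1.1 progression or death, set an origin common to both arms (randomisation or day 1), say which scan dates a progression confirmed later, and censor at new anticancer therapy.
3. **Response.** In 8.2, report RECIST 1.1 response at local and distant sites, using the non-target categories for participants without measurable disease. Report shrinkage at non-ablated sites separately, in participants who have such a lesion.
4. **Objective 3.3(1).** State that day-22 peri-ablation tissue does not compare pembrolizumab before and after HIFU. Either rest that comparison on the optional day-64 biopsies, as descriptive only, or reword the objective to the day-22 contrast.

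The cost is wording in 2.1, 4.4, 8.1 and 8.2, and in 3.3 if that objective is reworded. It needs no new visits, biopsies, scans or data.
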